9.1. Study period and study design

The analysis will be conducted using data from 01 January 2016 through 31 December 2021 or the latest available data at the time of extraction (i.e., the *study period*). Patients will be identified during a *selection window* of 01 January 2017 to 31 October 2021. The date of the first apixaban or LMWH prescription on or within the 30 days following a VTE diagnosis will be termed as the index date. Patients will be required to have continuous enrollment with medical and pharmacy benefits for 12-months prior to the index date to assess study eligibility criteria and to measure baseline characteristics (*the baseline or pre-index period*). Patients will also be required to have continuous enrollment with medical and pharmacy benefits for at least one month (30 days) starting on and following the index date (the follow-up or post-index period) and will be followed through the earliest of the following: health plan disenrollment, index therapy discontinuation, switch to another anticoagulant (includes switch to the other study medication or unfractionated heparin, fondaparinux, warfarin, rivaroxaban, dabigatran, or edoxaban), or end of study period (31 December 2021).

Note: Patients in the LMWH cohort will NOT be considered to have discontinued or switched if they change to an LMWH other than the index LMWH (dalteparin, enoxaparin, or tinzaparin).

Figure 1. Study Period

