 - c. Switching will be defined as a prescription for an anticoagulant other than the index apixaban/LMWH prescription (unfractionated heparin, fondaparinux, other OAC, or LMWH for patients indexed on apixaban; unfractionated

PFIZER CONFIDENTIAL

CT24-WI-GL02-RF02 4.0 Non-Interventional Study Protocol Template For Secondary Data Collection Study 01-Jun-2022

Page 17 of 35

090177e19b7d94e0\Approved\Approved On: 29-Aug-2023 01:40 (GMT)

Apixaban**B0661183 NON-INTERVENTIONAL STUDY PROTOCOL**

Protocol Version: 2.0 29 July 2022

heparin, fondaparinux, or OAC (including apixaban) for patients indexed on LMWH) within 30 days following discontinuation of the index medication.

Note: Patients indexed on LMWH cohort will NOT be considered to have discontinued or switched if they change to an LMWH other than the index LMWH (dalteparin, enoxaparin, or tinzaparin)

6. ≥ 18 years of age at index

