9.1.2. Exclusion criteria

Patients meeting any of the following criteria will be excluded from the study:

1. ≥ 1 claim with a ICD-10 diagnosis code of atrial fibrillation/flutter during the 12-month pre-index
2. ≥ 1 claim with a ICD-10 procedure code of mechanical heart valve during the 12-month pre-index
3. ≥ 1 claim with a ICD-10 diagnosis code of VTE diagnosis during the 12-month prior to index VTE encounter
4. ≥ 1 prescription claim of OAC or parenteral anticoagulant (PAC) (unless prophylactic) before the index VTE encounter
 - a. The OAC or PAC prescription claim will be considered prophylactic if duration of the prescription is ≤ 42 days AND the start date of OAC or PAC occurs within 2 days before or 7 days after knee/hip replacement surgery
OR
Start date of OAC or PAC occurred within 7 days after the admission of an hospitalization associated with 'medically ill' (primary discharge diagnosis; codes provided separately) AND with a ≥ 3 -day length of stay of the hospitalization
5. ≥ 1 claim with a ICD-10 procedure code or Common Procedural Terminology (CPT) code of inferior vena cava filter during the study period
6. ≥ 1 claim with a ICD-10 diagnosis code of antiphospholipid syndrome (APS) during the study period
7. ≥ 1 claim with a ICD-10 diagnosis code or procedure code (ICD-10 or HCPCS codes) of pregnancy during the study period
8. ≥ 1 prescription claim of an anticoagulant other than index apixaban or LMWH treatment between the index VTE encounter and index date. Other anticoagulants include heparin, fondaparinux, warfarin, dabigatran, rivaroxaban, and edoxaban
9. Data quality issues (with Medicare Cost coverage or State Children's Health Insurance Program (SCHIP), invalid year of birth or health plan enrollment dates) ('missing' will be reported for gender and region)

PFIZER CONFIDENTIAL

CT24-WI-GL02-RF02 4.0 Non-Interventional Study Protocol Template For Secondary Data Collection Study 01-Jun-2022

Page 18 of 35

090177e19b7d94e0\Approved\Approved On: 29-Aug-2023 01:40 (GMT)

Apixaban**B0661183 NON-INTERVENTIONAL STUDY PROTOCOL**

Protocol Version: 2.0 29 July 2022

A preliminary attrition table will be provided to Pfizer/Bristol Myers Squibb (BMS) for review, at which time modifications to the inclusion and exclusion criteria may be implemented.

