9.3.1. Baseline Measures

Baseline demographic/clinical characteristics will be descriptively reported for the Apixaban and LMWH cohorts, both pre- and post-IPTW. Demographic characteristics will be measured as of the patient's index date while clinical characteristics will be measured over the 1-year pre-index baseline period.

Demographic Characteristics

- Age (mean, standard deviation [SD], median, interquartile range [IQR])
- Age group (18-24, 25-34, 35-44, 45-54, 55-64, 65-74, ≥ 75 years; n, %)
- Gender (male, female, unknown/missing; n, %)
- Geographic region (Northeast, Midwest, South, West, unknown/missing; n, %)
- Payer type (commercial, Medicaid, Medicare Risk, self-insured, other/unknown; n, %)
- Health plan type (consumer directed health care, health maintenance organization [HMO], indemnity, point-of-service [POS], preferred provider organization [PPO], other/unknown; n, %)

PFIZER CONFIDENTIAL

CT24-WI-GL02-RF02 4.0 Non-Interventional Study Protocol Template For Secondary Data Collection Study 01-Jun-2022

Page 19 of 35

090177e19b7d94e0\Approved\Approved On: 29-Aug-2023 01:40 (GMT)

Apixaban

B0661183 NON-INTERVENTIONAL STUDY PROTOCOL

Protocol Version: 2.0 29 July 2022

- Index date year (2017, 2018, 2019, 2020, 2021; n, %)
- Follow up duration in months (mean, SD, median, IQR)
 - Patients censored due to switching (n, %)
 - Patients censored due to discontinuation (n, %)

Clinical Characteristics

- Prescriber physician specialty (associated with the visit on or closest to the index date, as available) (n, %)
 - Primary care physician (PCP - general practice/family practice/internal medicine)
 - Cardiologist
 - Oncologist
 - Others
 - Unknown/missing
- Index VTE event setting (n, %)
 - Inpatient
 - Total inpatient cost of index VTE hospitalization (mean, SD, median)
 - Length of stay (LOS) of index hospitalization (mean, SD, median)
 - Outpatient
 - Note: Qualifying outpatient encounters followed by qualifying inpatient encounters within 7 days will be considered an inpatient VTE event, unless LMWH or apixaban was initiated between encounters, in which case it will be classified as an outpatient VTE event
- Index VTE type (n, %)
 - DVT
 - PE
 - DVT and PE
- Charlson Comorbidity Index (CCI, Dartmouth-Manitoba adaptation excluding cancer; continuous and categorical [0-1, 2, 3, 4+]) (n, %)
- NCI comorbidity index (continuous and categorical [0-1, 2, 3, 4+]) (n, %)
- Comorbidities of interest (ICD-10 diagnosis codes; n, %)

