Due to the broad reach of the data, records in PharMetrics Plus are representative of the national, commercially insured population in terms of age and gender for individuals aged 65 and under. The data are also longitudinal, with more than 20 million patients who have both medical and pharmacy coverage with 3 or more years of continuous enrollment. Data contributions are subjected to a series of quality checks to ensure a standardized format and to minimize error rates. All data are Health Insurance Portability and Accountability Act (HIPAA)-compliant to protect patient privacy.

PharMetrics Plus will be largely commercially- or self-insured and may not be representative of un-insured or Medicare or Medicaid populations. Further research will be warranted to understand the costs of patient archetypes among these other populations, particularly those aged 65+ and covered by traditional fee-for-service Medicare. Additionally, there is a lack of visibility into HCRU or prescriptions obtained outside of the plan benefit.

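### Patients aged 65 or over are kept without any requirement that the plan be their main payer, so cost and inpatient events may be incompletely captured in them, and no analysis tests this

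*Combined protocol and SAP*

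**What the plan says.** All references are to the combined protocol and SAP.

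- **Age.** Section 9.1.1 requires only "≥ 18 years of age at index". Section 9.3.1 plans to report "Age group (18-24, 25-34, 35-44, 45-54, 55-64, 65-74, ≥ 75 years; n", so older patients are expected in both cohorts.
- **Payer.** Section 9.3.1 lists "Payer type (commercial, Medicaid, Medicare Risk, self-insured, other/unknown; n". The only exclusion based on coverage type is criterion 9 in section 9.1.2: "Data quality issues (with Medicare Cost coverage or" SCHIP, grouped there with invalid birth years and enrollment dates. No rule links age to payer type.
- **Enrollment.** Section 9.1 requires "continuous enrollment with medical and pharmacy benefits for 12-months prior to the index date" and at least 30 days from the index date.
- **Visibility.** Section 9.4 states that "there is a lack of visibility into HCRU or prescriptions obtained outside of the plan benefit". It describes the data as representative of commercially insured people up to age 65 and calls for further research in other populations, "particularly those aged 65+ and covered by traditional fee-for-service Medicare".
- **Outcomes.** Total all-cause cost is the sum of pharmacy, outpatient and inpatient cost (section 9.3.2), and comparing it is a primary objective (section 8). Recurrent VTE and major bleeding are identified from the primary discharge diagnosis of an inpatient claim (section 9.3.3).
- **Limitations.** Section 9.9 discusses generalizability beyond the commercially insured and judges that the limitations do not materially weaken the study.

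**The concern.** Being enrolled in a plan with medical and pharmacy benefits does not show that the plan pays first. If a patient aged 65 or over holds commercial or self-insured coverage while traditional Medicare is the main payer, an admission may reach this database with only part of its cost, or not at all. The patient then looks cheaper than they are. An unseen admission for recurrent VTE or major bleeding is also counted as no event and no event-related cost.

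This is a question of measurement inside the cohort, separate from whether the cohort represents other populations. It touches the primary cost outcomes and, through missing diagnoses, could also weaken the look-back exclusions for earlier VTE and atrial fibrillation.

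Propensity weighting does not solve it. If age and payer type enter the weights, the share of such patients can be balanced, but the missing dollars stay missing in both cohorts. Where medical cost is partly lost and pharmacy cost is seen more fully, the total leans towards drug cost, a component in which the two treatments may differ.

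**Working it through.** **1. The plan's own figures.** The only computed figures are the sample sizes in section 9.5. Formula, with pooled variance under the null, two-sided 5%, 80% power and no continuity correction:

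n = [1.960·√(2p̄(1−p̄)) + 0.8416·√(p₁(1−p₁) + p₂(1−p₂))]² / (p₁−p₂)²

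- 148/3,393 against 396/6,108: n = 1,788 per cohort, as stated.
- 5.6% against 7.9%: n = 1,867 per cohort, as stated.

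Both reproduce. They rest on recurrent VTE rates and say nothing about cost capture.

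**2. Is there a rule that closes the gap?**

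| Rule | What it ensures | What it leaves open |
|---|---|---|
| Continuous medical and pharmacy benefits (9.1) | The plan offers both benefits | Whether the plan is the main payer |
| One VTE claim, plus two cancer claims or one cancer and one treatment claim (9.1.1) | Some medical claims are visible | Whether the rest are |
| Exclusion 9 (9.1.2) | Medicare Cost and SCHIP are out | Age 65+ with commercial, self-insured or other/unknown payer |
| Age and payer tabulated (9.3.1) | Each is described by cohort | Not crossed; no restricted analysis |
| Stabilized IPTW (9.7) | Can balance age and payer type | Cannot restore missing cost |

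None of these requires the plan to be the main payer.

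**3. How large could it be?** The documents give no inputs, so everything below is assumed. Let s be the share of a cohort affected (the same in both) and v the visible fraction of their medical cost. With the same true mean in affected and unaffected patients, mean medical cost is multiplied by m = 1 − s(1−v).

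Illustrative monthly costs, apixaban against LMWH: medical $9,000 against $8,000, pharmacy $1,500 against $2,500. Both totals are $10,500, so the true ratio is 1.00. Pharmacy cost is taken as fully seen.

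| s | v | m | Apixaban | LMWH | Difference | Ratio |
|---|---|---|---|---|---|---|
| 10% | 0.2 | 0.92 | 8,280 + 1,500 = 9,780 | 7,360 + 2,500 = 9,860 | −$80 | 0.992 |
| 20% | 0.2 | 0.84 | 7,560 + 1,500 = 9,060 | 6,720 + 2,500 = 9,220 | −$160 | 0.983 |
| 30% | 0.2 | 0.76 | 6,840 + 1,500 = 8,340 | 6,080 + 2,500 = 8,580 | −$240 | 0.972 |
| 10% | 0.5 | 0.95 | 10,050 | 10,100 | −$50 | 0.995 |
| 20% | 0.5 | 0.90 | 9,600 | 9,700 | −$100 | 0.990 |
| 30% | 0.5 | 0.85 | 9,150 | 9,300 | −$150 | 0.984 |

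**4. Is the direction fixed?** No. Swap the two cohorts' costs and the v = 0.2 ratios become 9,860/9,780 = 1.008, 9,220/9,060 = 1.018 and 8,580/8,340 = 1.029. If apixaban were $1,000 lower on both components (8,000 + 1,500 against 9,000 + 2,500), the true difference of −$2,000 would shrink to −$1,760 at m = 0.76.

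**5. Unequal shares.** If the affected share differs between cohorts and total cost is captured at fraction v in affected patients, a true ratio of 1.00 becomes (1 − s_A(1−v))/(1 − s_L(1−v)). With 20% for apixaban and 10% for LMWH this is 0.84/0.92 = 0.913 at v = 0.2 and 0.90/0.95 = 0.947 at v = 0.5. With the shares reversed it is 1.095 and 1.056. With equal shares it stays 1.00. Successful weighting on age and payer would limit this part.

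**The case against.** The strongest reply is that no text places a patient with primary traditional Medicare in the cohorts. Section 9.4 names that group among populations the database may not represent, and payer order is an assumption. That stands, and it is why the conclusion is that capture may be incomplete, not that it is.

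Second, entry requires in-plan claims for VTE and cancer, so a patient whose medical claims never reach the database cannot enter. This makes very low visibility less likely, but the threshold is a few claims and does not show complete capture.

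Third, section 9.4 records both allowed and plan-paid amounts. If allowed amounts are used, more of the cost on claims paid second may be seen. The cost sections do not say which amount defines cost, so the point remains open.

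Fourth, section 9.4 does disclose the visibility limit, and for prescriptions as well. That weakens the assumption in the illustration that pharmacy cost is complete. The disclosure is still not connected to retained patients, and no analysis follows from it.

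A reader might infer that total cost cannot be measured at all in patients aged 65 or over, or that they are kept whatever their payer. The documents support neither: Medicare Cost coverage is excluded, Medicare Risk is a separate payer type, and the extent of capture elsewhere is not stated.

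**Conclusion.** The plan admits patients aged 65 or over without requiring that the plan be their main payer, acknowledges that outside care is invisible, and does not link the two. The primary cost outcomes and the inpatient-defined recurrent VTE and major bleeding outcomes may therefore be under-captured in any retained patient aged 65 or over whose main payer is traditional Medicare. Weighting cannot repair that.

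The size and direction are unknown. With 10-30% of each cohort affected and 20% of their medical cost visible, the illustration moves a true total cost ratio of 1.00 to about 0.99-0.97; with other cost patterns it moves the other way. A reader might take 1 − m = 8-24% as the bias in the result. That figure applies only to the medical component, under assumed inputs, and is not a finding about this study. Nor do the documents support a claim that LMWH is systematically made to look dearer.

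This justifies a low-cost addition to the plan. It does not establish that the primary analysis is invalid, or that all patients aged 65 or over outside Medicare Risk must be excluded: some may have a plan that pays first and complete costs.

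**What to change.** 1. In section 9.7, pre-specify a sensitivity analysis of the primary cost comparisons (all-cause, and related to recurrent VTE, major bleeding and CRNM bleeding). Restrict it to patients under 65 at index plus patients aged 65 or over whose payer type is Medicare Risk. Re-estimate the IPTW in that set. Define age from the available year of birth and state the rule for patients whose 65th birthday falls in the index year.
2. In section 9.3.1, add the age-by-payer table by cohort. This shows how many patients the question concerns.
3. In section 9.9, state that cost and events may be under-captured in retained patients aged 65 or over outside Medicare Risk.

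Age and payer type are already planned variables, so the programming cost is small. The price is a smaller sample and less precision in the restricted set. The feasibility count of 4,972 apixaban patients was taken before other criteria and no LMWH count is given, so attrition must show whether 1,788-1,867 per cohort still holds.

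One gap remains: patients just under 65 at index can pass 65 during follow-up. Ending follow-up at that birthday would need a birth date, and the documents mention only age and year of birth.

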9.2. Cohorts

From the overall cohort of VTE patients with cancer, two cohorts of interest will be created based on the type of anticoagulation treatment received within 30 days following the index VTE encounter date.

- **Cohort #1** – Apixaban: Evidence of apixaban use (and no other anticoagulant [LMWH, other OAC, heparin or fondaparinux] between the index VTE encounter date and index date).
- **Cohort #2** – LMWH: Evidence of LMWH use (and no apixaban or other anticoagulant between the VTE index date and LMWH initiation date).

LMWH should be used for at least 14 days to ensure that LMWH was not intended for short-term bridge therapy.

Analyses will be stratified by these two cohorts, as defined in section 8.3.1-8.3.3.

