9.1.1. Inclusion criteria

Patients must meet all of the following inclusion criteria to be eligible for inclusion in the study:

090177e19b7d94e0\Approved\Approved On: 29-Aug-2023 01:40 (GMT)

Apixaban

B0661183 NON-INTERVENTIONAL STUDY PROTOCOL

Protocol Version: 2.0 29 July 2022

1. Patients with ≥ 1 diagnosis code for VTE (inpatient [primary or secondary discharge diagnosis] or any position on an outpatient non-ancillary medical claim) between January 1, 2017 and October 31, 2021 (selection window).
 - Note: Qualifying outpatient encounters followed by qualifying inpatient encounters within 7 days will be considered an inpatient VTE event, unless LMWH or apixaban was initiated between encounters, in which case it will be classified as an outpatient VTE event
 - First date of claim with a VTE diagnosis code will be termed the ‘index VTE encounter’

2. Evidence of having active cancer, defined as ≥ 2 medical claims with a cancer diagnosis (excluding nonmelanoma skin cancer) on different days during the 6 months before or within 30-days after the index VTE event

OR

≥ 1 medical claim for a cancer diagnosis AND ≥ 1 claim for cancer treatment (eg: chemotherapy, radiation, immunotherapy, hormone therapy or cancer related surgery using national drug codes (NDC), international classification of diseases, tenth revision, clinical modification [ICD-10-CM] procedure codes or healthcare common procedure coding system [HCPCS] codes) during 6 months before or within 30 days after the index VTE encounter

3. ≥ 1 claim of apixaban or LMWH (dalteparin orenoxaparin) on or within 30 days following the index VTE encounter.
 - a. The date of the first apixaban or LMWH prescription fill will be designated as the index date
4. ≥ 12 months of continuous enrollment prior to the index date (pre-index)
5. ≥ 1 months of continuous enrollment including and following the index date (post-index)
 - a. Note: Each patient will have a variable follow-up period with a minimum of 1-month follow-up. Patients will be followed from the day after the index date through the earliest of the following: health plan disenrollment, index therapy discontinuation, switch to another anticoagulant, or study end (December 31, 2021).
 - b. Discontinuation will be defined as occurrence of a ≥ 30 day gap from the run-out of days’ supply of the index LMWH or apixaban prescription. The date of the discontinuation will be defined as the last day of the days’ supply of the last filled prescription.

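### The 14-day minimum-use rule applies to the LMWH cohort only, although both cohorts are followed from the first fill; read as actual use, it selects one cohort on post-index persistence

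*Combined protocol and SAP*

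**What the plan says.** Section 9.2 (Cohorts) defines the LMWH cohort by LMWH use and adds: "LMWH should be used for at least 14 days to ensure that LMWH was not intended for short-term bridge therapy". The apixaban cohort needs only "Evidence of apixaban use (and no other anticoagulant [LMWH, other OAC, heparin or fondaparinux] between the index VTE encounter date and index date". Sections 9.1.1 and 9.1.2 set no minimum duration of apixaban use.

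Time zero is common to both cohorts. Under criterion 3 of section 9.1.1, "The date of the first apixaban or LMWH prescription fill will be designated as the index date". Note 5a states: "Patients will be followed from the day after the index date". It ends observation when a patient leaves the plan, stops the index drug, changes anticoagulant or reaches the end of 2021, whichever comes first. Follow-up is therefore on-treatment. Note 5b dates discontinuation to the day on which the supply from the final fill runs out, so on-treatment time can be short.

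Section 9.3.2 turns each patient's cost into a monthly figure by dividing by that patient's follow-up days and multiplying by 30.

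The plan contains no landmark, no apixaban counterpart to the 14-day rule, no sensitivity analysis without it, and no mention of it in section 9.9 (Limitations).

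**The concern.** Whether a patient used LMWH for 14 days is known only after the index date, and those 14 days lie inside the period in which costs and events are counted. If the rule is applied to actual use, membership of one cohort depends on what happens during follow-up. An LMWH patient who stops or switches on day 8, for whatever reason, leaves the study with all costs and events to that point. An apixaban patient with the same course stays and is counted.

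Two things follow. Some early events are removed from one cohort only, namely those that end LMWH use before day 14. And LMWH patients receive a guaranteed minimum of on-treatment time, which enters the denominator of the monthly cost. Both primary objectives, all-cause cost and event-related cost, use these data.

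**Working it through.** **1. Do other provisions even out the cohorts?**

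- *30-day requirement.* Section 9.1, criterion 5 and section 9.3.2 all express it as enrollment. A patient can be enrolled for 30 days and on treatment for 7. Note 5a also speaks of one month as the minimum follow-up, but then ends follow-up at discontinuation or switch. Enrollment is the better-supported reading.
- *7-day exclusion of early recurrences (section 9.3.3).* It applies to both cohorts, runs from the index VTE and covers recurrent VTE only. Bleeding and all-cause cost are untouched.
- *Weighting (sections 9.3 and 9.7).* Stabilized weights balance measured baseline characteristics. They cannot restore patients excluded for post-index behaviour.

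**2. Monthly cost.** Formula from section 9.3.2: cost / days × 30. The protocol's own example reproduces: $10,000 / 60 × 30 = $5,000. The multiplier is 30/days.

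| On-treatment days | Multiplier | $10,000 becomes |
|---|---|---|
| 5 | 6.00 | $60,000 |
| 7 | 4.29 | $42,857 |
| 14 | 2.14 | $21,429 |

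With the rule applied as on-treatment days, LMWH patients cannot lie above the last row. Apixaban patients can.

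**3. Events.** The documents give no rate of LMWH stopping before day 14, so every input here is an assumption. Take the same true risk in both cohorts: 1% of starters have a first event in days 1-14, and 2% would have one later if they stayed on treatment. Let k be the share of early events that end LMWH use before day 14, and s the share of starters in each cohort who stop by day 14 without an event.

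- Apixaban recorded risk = 1% + 2% × (1 − s)
- LMWH recorded risk = [1% × (1 − k) + 2% × (1 − s)] / [1 − s − 1% × k]

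Example, s = 20% and k = 25%: apixaban 1.0% + 1.6% = 2.6%; LMWH (0.75% + 1.6%) / (1 − 0.20 − 0.0025) = 2.35% / 0.7975 = 2.95%; ratio 1.13.

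| s | Apixaban | LMWH/apixaban ratio, k = 25% | k = 50% | k = 100% |
|---|---|---|---|---|
| 0% | 3.0% | 0.92 | 0.84 | 0.67 |
| 10% | 2.8% | 1.01 | 0.92 | 0.72 |
| 20% | 2.6% | 1.13 | 1.02 | 0.78 |

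The true ratio is 1 in every cell. The rule alone moves it, in either direction. Removing early events lowers the LMWH figure. Removing event-free early stoppers raises it, because those who remain have more on-treatment time in which to record a later event.

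**The case against.** Excluding bridging is a legitimate aim, and the rule is undefined rather than plainly wrong. Its stated purpose concerns what LMWH was intended for, and it could mean days' supply on the index fill. That is known at time zero, and selection on later behaviour would largely disappear. Even if use is measured after index, the supply-based definition of discontinuation means that a patient with a 14-day fill who bleeds on day 5 and stops may still count as a user. Selection would then fall mainly on short, unrefilled first fills and on early switches. This all stands. It makes the size uncertain and shows that the rule needs a definition, but on either reading the rule is one-sided.

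A reader might infer that every LMWH patient with an early bleed or admission is dropped. The text does not support that: the condition is on use, not on events.

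A reader might also infer that the bias must favour LMWH. The table shows that the sign depends on how many patients stop early without an event. In addition, patients bridged from LMWH to apixaban cannot enter the apixaban cohort. If they are healthier than average, removing them from the LMWH cohort could leave it sicker.

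The 30-day enrollment rule and the 7-day recurrence exclusion remove some early events from both cohorts. That narrows the problem without removing it.

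**Conclusion.** The asymmetry holds: one cohort has a minimum-use condition, the other has none, both are counted from the first fill, and no planned analysis corrects for it. The limit on the LMWH multiplier (2.14, against 4.29 for an apixaban patient with 7 days) follows from the protocol's formula, provided the rule is applied as on-treatment days. How often apixaban follow-up is that short is not stated.

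The effect on event comparisons can be bounded only by assumption. With equal true risks of 1% early and 2% later, and the ranges of k and s above, the spurious ratio runs from about 0.67 to 1.13; k = 100% is an extreme. The documents support neither a claim that the bias favours one drug nor a single estimate of its size. No effect on cost has been estimated beyond the multiplier. An uncertain direction does not make the comparison sound, and because the rule defines a cohort for both primary objectives, it should be settled before analysis.

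**What to change.** - State how 14 days of use is measured.
- Apply the same 14-day on-treatment requirement to both cohorts, and count costs, events and person-days from day 15 in both (a landmark analysis).
- Report the number excluded by the rule in each cohort.
- Keep the current one-sided rule as a sensitivity analysis. A second one can define the rule by days' supply known at the index fill, in both cohorts.
- State that the one-month minimum in note 5a means enrollment, in line with sections 9.1 and 9.3.2.

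This needs protocol wording and an eligibility flag, and no new data; section 9.1.2 already allows the criteria to be revised at the attrition review. The landmark gives up the first 14 days of outcomes and some patients in both cohorts, and its results then apply to patients still on the index drug at day 14. The index-fill version keeps some bridging patients and drops patients treated continuously through serial short fills.
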